### 4.4.2 Exclusion Criteria

1. Subject currently has a spinal cord stimulation system implanted.
2. Subject has previously failed SCS therapy (either trial system evaluation or permanent implant).
3. Subject has a primary diagnosis for SCS implantation of Peripheral Vascular Disease (PVD), Angina Pectoris, or Chronic Migraine.
4. Subject has or plans to have a Peripheral Nerve Stimulation system (PNS), Peripheral Nerve field Stimulation system (PNfS), Dorsal Root Ganglion system (DRG), or implantable infusion pump.
5. Subject is currently participating in another clinical investigation with an active treatment arm.
6. Subject is unable to read and/or write.

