Previous studies using BurstDR have examined the safety and efficacy of the stimulation mode for patients who were already using tonic stimulation . These studies reported favorable outcomes for the new stimulation mode, with many patients achieving greater pain control and experiencing less paresthesia with BurstDR compared to tonic stimulation. Currently, the body of evidence for BurstDR is limited to subjects with prior experience using tonic stimulation. Patients who trial the SCS system with tonic stimulation may be conditioned to associate paresthesia with pain relief. When the patient then switches to BurstDR stimulation, the lack of paresthesia may violate that previous association and reduce the potential benefit of treatment. The SUNBURST trial  provides some evidence that this may be the case. In the trial, BurstDR stimulation was shown to provide more pain relief than tonic stimulation, but 22% of the patients who failed to achieve at least 30% pain reduction with BurstDR did achieve clinically relevant pain relief with tonic stimulation. It is possible that these patients would have responded to BurstDR had they not previously been conditioned to tonic stimulation. Data regarding patients who use BurstDR stimulation from the beginning of their exposure to SCS is necessary to fully evaluate any qualitative or quantitative differences in therapy outcomes for the two waveforms.

The SUNBURST trial in the US and PRODIGY I PMCF in Europe demonstrated clinically meaningful pain reduction with BurstDR at one year; however, no studies to date have reported outcomes beyond 12 months. Longer-term follow-up is needed to demonstrate sustainable pain relief over time.

For devices that deliver both tonic and BurstDR waveforms, individual patient characteristics (e.g. pain history, mental/physical health, and sensory experience) may affect the way a patient achieves maximum

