benefit from the therapy. After an initial crossover period, SUNBURST allowed patients to select the program mode (tonic or BurstDR) according to individual preference during the follow-up period. Approximately 60% of subjects used BurstDR most frequently at one year, while the other 40% used some combination of tonic and BurstDR programs. The relationships between program usage patterns, patient characteristics, and long-term outcomes have yet to be examined for these multi-waveform SCS devices. Exploring these relationships will likely provide valuable insight into patient needs and enhance clinical care decisions.

Given the evidence gaps described above for BurstDR and multi-waveform devices, the goals of the current study are: to assess pain relief for BurstDR stimulation when presented as the initial SCS experience, assess long-term outcomes for BurstDR, and to explore the relationship between program usage patterns, patient characteristics, and therapy outcomes.

Figure 1: Tonic pattern

[figure not shown]
[figure not shown]

Figure 2: BurstDR pattern

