## 4.4 Study Population

The patient population enrolled in this study will be comprised of male and female patients. Patients must meet the specific eligibility criteria to participate in the study.

A patient, who meets all inclusion criteria, and none of the exclusion criteria, is eligible to participate in this study.

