### 4.4.1 Inclusion Criteria

1. Subject has chronic, intractable pain of the trunk and/or limbs, including unilateral or bilateral pain associated with the following: failed back surgery syndrome and intractable low back and leg pain.
2. Subject has a score of 6 or higher on the NRS for average pain specific to the area(s) of chronic pain being treated over the past 24 hours at the baseline visit.
3. Subject is considered by the Investigator as a candidate for implantation of a spinal cord stimulator system according to the system Instructions for Use.
4. Subject is 18 years of age or older at the time of enrollment.
5. Subject is willing to cooperate with the study requirements including compliance with the regimen and completion of all study visits.
6. Subject has signed and received a copy of the Ethics Committee/Institutional Review Board (EC/IRB) approved informed consent.

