### **5.3.2 Trial System Implant**

(In clinic, prior to permanent implantation, within 3-45 days from Baseline visit)

Subjects must undergo a successful trial system evaluation of the SCS system prior to permanent implantation of the SCS system. It is a requirement that the subjects will be trialed with BurstDR and only a BurstDR program will be provided to, and used by, the subject. In case of an on-the-table trial evaluation (aka all-in-one procedure), the pain mapping can be done with tonic. The trial system evaluation procedure will be conducted according to the national standards and guidelines. The SCS Trial System Evaluation visit will include recording the following:

- Trial System implant and system information
- Adverse Events (if applicable)
- Deviations (if applicable)
- Withdrawal (if applicable)
- Death (if applicable)

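### Eligibility does not require SCS-naive patients, although one of the three stated goals is to assess BurstDR as the first SCS experience

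*Combined protocol and SAP*

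**What the plan says.** Section 2 sets out the evidence gap: "Currently, the body of evidence for BurstDR is limited to subjects with prior experience using tonic stimulation". It explains why this matters: "Patients who trial the SCS system with tonic stimulation may be conditioned to associate paresthesia with pain relief", so that a later change to a waveform without paresthesia may bring less benefit. The first of the three goals that follow is "to assess pain relief for BurstDR stimulation when presented as the initial SCS experience".

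Section 4.4.2 has two exclusions on SCS history. Exclusion 1 reads "Subject currently has a spinal cord stimulation system implanted". Exclusion 2 covers failures: "Subject has previously failed SCS therapy (either trial system evaluation or permanent implant". The other four exclusions concern primary diagnosis, other implanted neuromodulation or pumps, participation in another study, and literacy.

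None of the six inclusion criteria in Section 4.4.1 asks for an SCS-naive patient. The nearest is "Subject is considered by the Investigator as a candidate for implantation of a spinal cord stimulator system according to the system Instructions for Use". Section 4.4 makes the listed criteria sufficient: "A patient, who meets all inclusion criteria, and none of the exclusion criteria, is eligible to participate in this study".

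**The concern.** Section 2 treats earlier tonic exposure as the feature of past BurstDR studies that this study should avoid. The eligibility criteria do not avoid it fully. Exclusion 2 mentions both earlier trials and earlier implants, so the authors had previous exposure in view, but they made exclusion depend on its outcome.

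What is at stake is how the first goal can be reported. Section 6.1.1 (Primary Endpoint) plans a descriptive comparison with existing tonic and BurstDR trials. That comparison speaks to first exposure only if this cohort is SCS-naive or its naive members can be identified. As written, neither is assured.

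**Working it through.** **Step 1. Walk each SCS history through the criteria.**

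| SCS history before consent | Criterion that applies | Result |
|---|---|---|
| None | none | eligible |
| System now implanted | exclusion 1 | excluded |
| Earlier trial, failed | exclusion 2 | excluded |
| Earlier implant, failed | exclusion 2 | excluded |
| Earlier trial successful, never implanted | none | eligible |
| Earlier implant removed for a reason other than failure | none | eligible |

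The last two rows are the gap. Exclusion 2 does not define failure, so sites may draw the line in different places.

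**Step 2. Look for another safeguard.**
- Section 5.3.2 makes the study's own trial BurstDR-only. That governs stimulation after enrolment, not before it.
- Section 5.3.1 collects pain history at baseline but does not name previous SCS exposure or waveform. The CRFs are under separate cover (Appendix E), so they may record it.
- The Subgroup Analysis section (numbered 6.1.1, after 6.1.4) stratifies by on-the-table trial versus BurstDR trial. There is no split by previous SCS exposure.

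**Step 3. Reproduce the plan's figures (Section 6.3).** Inputs: 267 enrolled, 10% lost between baseline and trial, 30% trial failure, 14% lost from implant to 6 months, SD of the NRS change 3.
- Implanted: 267 × 0.90 × 0.70 = 168.2 (plan: 168).
- Evaluable at 6 months: 168.2 × 0.86 = 144.7 (plan: 145).
- Half-width: 1.96 × 3 / √145 = 0.488, or 0.492 with the t distribution on 144 degrees of freedom (plan: 0.49).

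All three agree. The point disputes none of them, and a criterion applied at screening leaves them unchanged.

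**Step 4. Illustrate the size.** The documents do not give the share f of evaluable subjects with earlier SCS, nor the difference d between their mean NRS change and that of naive subjects. Both are assumptions here: f from 1% to 20%, with 1% to 5% the more plausible part, and d from 0.5 to 2 points in either direction. The SD is kept at 3.
- Subjects affected = 145 × f.
- Half-width in naive subjects = 1.96 × 3 / √(145 × (1 − f)).
- Shift in the overall mean = f × d.

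| f | Affected | Naive | Half-width | Shift, d = 0.5 to 2 |
|---|---|---|---|---|
| 1% | 1.45 | 143.55 | 0.491 | 0.005 to 0.02 |
| 2% | 2.9 | 142.1 | 0.493 | 0.01 to 0.04 |
| 5% | 7.25 | 137.75 | 0.501 | 0.025 to 0.10 |
| 10% | 14.5 | 130.5 | 0.515 | 0.05 to 0.20 |
| 20% | 29 | 116 | 0.546 | 0.10 to 0.40 |

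Up to 5%, the shift is at most 0.10 points, against a planned half-width of 0.49. Only the extreme corner (20% and 2 points) comes near that half-width.

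**The case against.** The strongest reply is that first exposure is not what the study formally estimates. It is one of three goals in the background section. The primary objective in Section 4.2.1 concerns pain relief with a multiple-waveform device and does not mention first experience. Section 5.3.4 allows tonic, BurstDR or both from permanent implant, so the 6-month NRS change was never a pure BurstDR estimate. The analysis is descriptive, and Section 6.2 presents the study as real-world experience. All of this stands. It limits the point to the first goal but does not close the gap.

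The group left in is also narrow, and a broad reading of failure by sites would narrow it further. That stands too.

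A reader might infer that admitting earlier responders while excluding failures pushes the mean toward benefit. The documents do not support a direction. The conditioning argument in Section 2 points the other way. Moreover, Sections 5.3.2 and 5.3.3 already restrict implanted subjects to those who passed the in-study BurstDR trial, so an earlier success adds little further selection.

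A reader might also infer that every such patient is conditioned to tonic stimulation. Section 2 says only that this may happen. Earlier SCS need not have been tonic, since the BurstDR-capable systems in Section 3.1 are market released.

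**Conclusion.** The gap is real on the text: patients with earlier SCS that did not fail can enter, and the plan neither excludes them nor separates them in analysis. This is a mismatch between one stated goal and the population, and it holds whichever way the mean might move.

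Its size is probably small. The figure of about 1 to 7 of 145 subjects rests on an assumed share of 1% to 5%, and the mean shift of at most 0.10 points rests in addition on an assumed difference of up to 2 points. The primary objective is not contradicted, and these illustrations give no reason to regard the primary NRS estimate as materially distorted. It also cannot be asserted that previous SCS exposure goes unrecorded, because the CRFs are not part of the document. The point is worth acting on because the correction is cheap and lets the study answer its own first question.

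**What to change.** Reword exclusion 2 to exclude any previous SCS exposure, trial or permanent, whatever the outcome. This also removes the need to define failure for that criterion. The cost is a few otherwise eligible patients; the planned 267, 168 and 145 do not change.

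If enrolment is too advanced for that:
- Record previous SCS exposure and its waveform at baseline, if the CRF does not already do so.
- Report the 6-month NRS change in SCS-naive subjects as well as in all evaluable subjects.
- Base any statement about BurstDR as a first SCS experience on the naive group.

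The cost is at most one baseline field, one extra summary and a slightly wider interval (half-width about 0.50 instead of 0.49 if an assumed 5% are left out).

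Neither option removes the tonic pain mapping that Section 5.3.2 permits in on-the-table trials. That is a separate exposure, and the planned subgroup analysis already reports those subjects apart.

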## 5 Procedures

The clinical study will be conducted in accordance with the CIP. All parties participating in the conduct of the clinical study will be qualified by education, training, or experience to perform their tasks and this training will be documented appropriately.

The clinical study will not commence until Abbott receives written approval from the IRB/EC and relevant regulatory authorities and all required documents have been collected from the site(s).

The following sections provide a detailed description of procedures required by this CIP.

### 5.1 Informed Consent Process

The Principal Investigator (PI) or his/her authorized designee will conduct the Informed Consent Process, as required by applicable regulations and the center's IRB/EC. This process will include a verbal discussion with the subject on all aspects of the clinical investigation that are relevant to the subject's decision to participate, such as details of clinical investigation procedures, anticipated benefits, and potential risks of clinical investigation participation. During the discussion, the Principal Investigator or his/her authorized

designee will avoid any improper influence on the subject and will respect subject's legal rights. The subject shall be provided with the informed consent form written in a language that is understandable to the subject and has been approved by the center's IRB/EC. The subject shall have adequate time to review, ask questions and consider participation.

If the subject agrees to participate, the Informed Consent form must be signed and dated by the subject and by the person obtaining the consent. The signed original will be filed in the subject's hospital or research charts, and a copy will be provided to the subject.

The Principal Investigator or his/her authorized designee will document the informed consent process in the subject's hospital and/or research charts. The date of signature will be entered on an applicable Case Report Form (CRF).

Failure to obtain informed consent from a subject prior to clinical investigation enrollment should be reported to Sponsor within 5 working days and to the reviewing center's IRB/EC according to the IRB's/ EC's reporting requirements.

If, during the clinical investigation, new information becomes available that can significantly affect a subject's future health and medical care, the Principal Investigator or his/her authorized designee will provide this information to the subject. If relevant, the subject will be asked to confirm their continuing informed consent in writing.

## **5.2 Point of Enrollment**

Patients are considered enrolled in the study from the moment the patient has provided written Patient Informed Consent (Refer to section 5.1 for the Informed Consent Process).

## **5.3 Scheduled Procedures**

The Principal Investigator is responsible for ensuring all clinical investigation data is collected as required per CIP scheduled procedures.

### **5.3.1 Baseline**

(in clinic, visit must be completed minimum 3 days and max 45 days before the trial system evaluation)

The following activities must occur before any study procedure/visit.

- The Principal Investigator or delegated study personnel is responsible for screening all potential patients to determine patient eligibility for the study.
- If a patient meets all inclusion criteria and does not meet any of the exclusion criteria, he/she is eligible for the study.
- The patient is enrolled in the study when the patient signed the EC/IRB approved Informed Consent form.

Record enrollment information (name of the study, date of consent and Inclusion/Exclusion information) in the hospital records and complete the Baseline CRF electronically preferably within 5 days after enrollment. Notification of enrollment to the Sponsor will take place only when the Sponsor receives the Baseline CRF.

NOTE: As soon as the patient signs the Patient Informed Consent form, all Adverse Device Effects and all Serious Adverse Events need to be reported according to the guidelines mentioned in this CIP (refer to section 8.2).

In case the subject was consented to participate in the study, but does not meet inclusion/exclusion criteria, and was not implanted, the subject should be withdrawn and a withdrawal form must be completed. The patient will resume his/her regular standard of care with his/her physician.

In case the subject was consented to participate in the study and was implanted but does not meet inclusion/exclusion criteria, then this is considered a protocol violation. A protocol deviation form needs to be completed and the Sponsor must be informed. The EC/IRB and Competent Authority (CA), if applicable, should be notified appropriately about any deviations with regards to the violation of inclusion/exclusion criteria.

The following information will be collected at the baseline visit:

- Demographics, Pain History, Pain Primary/Secondary Diagnosis, occupational/lifestyle information
- NRS
- Other Patient Reported Outcome Measures (EQ5D questionnaire, PCS, STAI, PHQ9, TSK, MOS Sleep Scale, PROMIS Physical Function scale, Pain Location).
- Chronic Pain related medication usage
- Adverse Events (if applicable)
- Deviations (if applicable)
- Withdrawal (if applicable)
- Death (if applicable)

### **5.3.2 Trial System Implant**

(In clinic, prior to permanent implantation, within 3-45 days from Baseline visit)

Subjects must undergo a successful trial system evaluation of the SCS system prior to permanent implantation of the SCS system. It is a requirement that the subjects will be trialed with BurstDR and only a BurstDR program will be provided to, and used by, the subject. In case of an on-the-table trial evaluation (aka all-in-one procedure), the pain mapping can be done with tonic. The trial system evaluation procedure will be conducted according to the national standards and guidelines. The SCS Trial System Evaluation visit will include recording the following:

- Trial System implant and system information
- Adverse Events (if applicable)
- Deviations (if applicable)
- Withdrawal (if applicable)
- Death (if applicable)

### **5.3.3 End of Trial System Evaluation**

(In clinic, prior to permanent implantation, timing in accordance with physician standard operation procedures)

If the trial system evaluation is unsuccessful, per standard of care, the subject is considered as a trial system failure and must be withdrawn from the study (withdrawal date is the date when the trial system evaluation ended). The End of Trial System Evaluation visit will include recording the following:

- Trial system evaluation conclusion information, patient reported pain relief and patient satisfaction
- Patient Reported Outcome Measures (NRS, PGIC)
- Programming information and program usage including programming parameters record
- Adverse Events (if applicable)
- Deviations (if applicable)
- Withdrawal (if applicable)
- Death (if applicable)

### 5.3.4 Permanent System Implant

(In clinic, timing in accordance with physician standard operation procedures)

Implantation of the SCS system will be performed according to standard operating procedures and will occur after a successful trial system evaluation period. Subjects will receive a patient programmer and will be instructed on how to use the system to relieve their pain. Subjects will be able to adjust the stimulation in order to generate the best results. Following system implantation, the stimulator will be activated and programmed by trained personnel and/or an Abbott representative either during post-operative recovery or at an office visit in accordance with the physician's and hospital's standard operating procedures. As of permanent implant, the subject can be stimulated with both tonic and/or BurstDR waveforms. The SCS system implantation will include recording of the following:

- Permanent system implant and system information
- Adverse Events (if applicable)
- Deviations (if applicable)
- Withdrawal (if applicable)
- MRI information (if applicable)
- Death (if applicable)

### 5.3.5 3-Month Follow-up Visit

± (In clinic, 3 months post-permanent implant +/-30 days)

Enrolled and permanent system implanted subjects will be evaluated at 3 months post-permanent implantation of the SCS system. In case the subject requires reprogramming, it should be performed before the print-out of the current programming parameters record and prior to any study visit assessments. During the visit, the following evaluations and procedures will be performed.

- Occupational/lifestyle information
- NRS, PGIC, patient satisfaction, patient reported pain relief, battery usage
- Other Patient Reported Outcome Measures (PCS, TSK, Stimulation Assessment, Pain Location)
- Programming information and program usage including programming parameters record
- Chronic Pain related medication usage
- Adverse Events (if applicable)
- Deviations (if applicable)
- Withdrawal (if applicable)
- MRI information (if applicable)
- Death (if applicable)

### 5.3.6 6-Month Follow-up Visit

This visit should be conducted in-clinic 6 months (±30 days) post-permanent implant.

Subjects with a permanent implant will be evaluated 6 months after initial permanent system implant. In case the subject requires reprogramming, it should be performed before the printout of the current programming parameters record and prior to any study visit assessments. During the visit, the following evaluations and procedures will be performed.

- Occupational/life style information
- NRS, PGIC, patient satisfaction, patient reported pain relief, battery usage
- Other Patient Reported Outcome Measures (EQ5D questionnaire, PCS, STAI, PHQ9, TSK, MOS sleep scale, PROMIS physical function scale, Pain Location, Stimulation Assessment)
- Programming information and program usage including programming parameters record
- Chronic Pain related medication usage

- Adverse Events (if applicable)
- Deviations (if applicable)
- Withdrawal (if applicable)
- MRI information (if applicable)
- Death (if applicable)

